#### 4.2.3 Venous Subjects

- Percent of treated vessels with ≥75% clot reduction from pre-JETi venogram to post-JETi venogram (post-JETi thrombectomy and before any adjunctive therapies to treat underlying culprit lesions) via modified Marder score. The independent imaging core laboratory will be responsible for assessing this endpoint.
- For subjects not treated for lower extremity DVT as defined in Appendix II (i.e., upper extremity DVT (UE DVT)), Clot removal grade for each JETi-treated target vessel from pre-JETi venogram to final venogram (post-JETi thrombectomy and after any/all adjunctive therapies and prior to removal of the vascular sheath) per the grades in Table 1.

 de Donato G, Pasqui E, Sponza M, et al. Safety and Efficacy of Vacuum Assisted Thrombo-Aspiration in Patients with Acute Lower Limb Ischaemia: The INDIAN Trial. *Eur J Vasc Endovasc Surg.* 2021;61(5):820-828. doi:10.1016/j.ejvs.2021.01.004

- Components of the JETi-related MAE up to 30 days post-JETi adjudicated by a CEC including death, symptomatic pulmonary embolism (PE), major bleeding, and re-thrombosis of JETi treated vessel(s).
  - Re-thrombosis of the JETi-treated vessel(s) at 30-day, and 12-month follow up, as assessed by investigator/physician reported, and as adjudicated by CEC.
  - The Villalta Post Thrombotic Syndrome (PTS) severity scale at baseline, 30-day, and 12-month follow-up. Note that this assessment will apply only to subjects with lower extremity DVT.
    - Edema component score from the Villalta Post Thrombotic Syndrome (PTS) severity scale at baseline, 30-day, and 12-month follow-up
  - A 7-point Likert Scale for leg pain at baseline, discharge, 30-day, and 12-month follow-up.
  - Venous patency and compressibility as determined by duplex ultrasound at baseline 30-day, and 12-month follow-up.
  - Acute success, [REDACTED] assessed by core laboratory:
    - Device success: post-JETi thrombus removal grade II-III [REDACTED]
    - Technical success: Final thrombus removal grade II-III, [REDACTED] where final [REDACTED] evaluation occurs after JETi system and any other adjunctive device or procedures.
    - Procedural success: Technical success with no JETi-related MAEs within 5 days of registration or by discharge, whichever occurs first.
- If no adjunctive therapies or devices are used after JETi, post-JETi [REDACTED] score is also final [REDACTED] score.
- [REDACTED]

## 5.0 SUBJECT SELECTION AND WITHDRAWAL

### 5.1 Subject Population

This Registry will register subjects of all genders from the patient population undergoing percutaneous treatment of thrombosis in the peripheral vascular system.

## 5.2 Subject Recruitment/Screening and Informed Consent

### 5.2.1 Subject Recruitment and Screening

A member of the site's study team previously trained to the CIP should evaluate patients for the general study eligibility criteria. A patient who does not satisfy all general eligibility criteria prior to informed consent is considered a recruitment failure and should not be enrolled in the Registry.

Sites will ask patients meeting general inclusion criteria and no general exclusion criteria to sign an Informed Consent Form (ICF) following the established Informed Consent process (described in **Section 5.2.2**) if they wish to participate in the Registry.

Enrolled (consented) subjects who do not have a JETi Catheter introduced into the intended vasculature are considered a screen failure and should be withdrawn from the Registry.

### 5.2.2 Informed Consent

The Investigator or his/her authorized designee (if applicable) will conduct the Informed Consent process, as required by applicable regulations and the center's IRB/EC. This process will include a verbal discussion with the patient on all aspects of the Registry that are relevant to the patient's decision to participate, such as details of registry procedures, anticipated benefits, and potential risks of registry participation. Sites must inform patients about their right to withdraw from the Registry at any time and for any reason without sanction, penalty, or loss of benefits to which the patient is otherwise entitled. Withdrawal from the Registry will not jeopardize their future medical care or relationship with the investigator.

During the discussion, the Principal Investigator or his/her authorized designee will avoid any improper influence on the patient and will respect patient's legal rights. Financial incentives will not be given to patients. Patients may be compensated for time and travel directly related to the participation in the Registry. The site shall provide the patient with the Informed Consent form written in a language that is understandable to the patient and that has been approved by the center's IRB/EC. The patient shall have adequate time to review, ask questions, and consider participation. The Principal Investigator or his/her authorized designee will make efforts to ensure that the patient understands the information provided. If the patient agrees to participate, they must sign and date the Informed Consent form, along with the person obtaining the consent prior to any registry-specific procedures. The site will file the signed original in the patient's hospital or research charts and provide a copy to the patient. The dated signatures can be electronic. The site will follow local hospital and local EC/IRB provisions for documenting electronic ICF signature.

Sites should report any failure to obtain informed consent from a patient to the Sponsor within 5 working days and to the reviewing center's IRB/EC according to the IRB's/ EC's reporting requirements.

If, during the Registry, new information becomes available that can significantly affect a subject's future health and medical care, the Principal Investigator or his/her authorized designee (if applicable) will provide this information to the subject. If relevant, sites will ask the subject to confirm their continuing informed consent in writing.

### 5.2.2.1 Special Circumstances for Informed Consent

Sites may enroll individuals who are unable to make the decision to participate in a registry on their own. Sites will obtain informed consent from the patient's legally authorized representative and will inform the patient about the Registry within his/her ability to understand. During the informed consent discussion, the Principal Investigator or his/her authorized designee will avoid any improper influence and make sure there is no manipulation of the patient and patient's legal rights are respected. Enrollment of these patients is important as data of comparable validity cannot be obtained from clinical research involving persons able to give informed consent or by other research methods. Additionally, the Registry directly relates to a medical condition from which the individual suffers, and the Registry is expected to produce a direct benefit to the individual, outweighing the risks and burdens involved.

The legally acceptable representative will represent the individual during the Informed Consent process, which will be performed according to the requirements in **Section 5.2.2**. Sites will respect the explicit wish of the individual to decline participation or withdraw from the Registry at any time. In addition, no incentives or financial inducements will be provided to these patients or their legally authorized representatives for their participation in the Registry.

This Registry excludes individuals under the age of 18 or age of legal consent from the Registry population.

Sites may enroll individuals unable to read or write in this Registry. Sites will obtain informed consent through a supervised oral process. An independent witness will be present throughout the Informed Consent process. A member of the site's study team previously trained to the CIP will read the written Informed Consent form and any other information aloud and explain to the prospective subject or his/her legally acceptable representative and will sign and personally date the Informed Consent form. The witness will also sign and personally date the Informed Consent form attesting that the information was accurately explained, and that informed consent was freely given. In addition, no incentives or financial inducements will be provided to these patients or their legally authorized representatives for their participation in the Registry.

Sites may enroll women who are pregnant or breastfeeding in this registry. Informed consent must be obtained using the IRB/EC approved informed consent in accordance with IRB/EC requirements. The Registry is expected to produce a direct benefit to the woman or her embryo, fetus, or child, outweighing the risks and burdens involved. When breastfeeding women are included, care shall be taken to avoid any adverse impact to the health of the child. In addition, no incentives or financial inducements will be provided to these patients or their legally authorized representatives for their participation in the Registry. All other aspects of the Informed Consent process will follow **Section 5.2.2**.

Sites may enroll individuals admitted to the emergency units in this Registry in cases where emergent removal of life- or limb-threatening thrombi in the peripheral vasculature is required. When prior informed consent of the individual is not possible because of the patient's medical condition, sites will request the informed consent of the subject's legally acceptable representative, if present. When it is not possible to obtain prior informed consent from the subject, and the subject's legally acceptable representative is not available, sites will perform the informed consent process in accordance with **Section 5.2.2** as soon as possible. In addition, patients are able to enroll in the Registry up to 5 days post-procedure.

In addition, sites must obtain an authorization for use and disclosure of the subject's protected health information, in accordance with the Health Insurance Portability and Accountability Act (HIPAA), from the subject or their legally acceptable representative.

For live cases at congresses, the patient needs to sign a specific Live Case ICF, approved by the IRB/EC. The investigator must notify the Sponsor prior to performing a live case.

## **5.3 Eligibility Criteria**

### **5.3.1 General Eligibility Criteria**

Assessment for general eligibility criteria is based on medical records of the site and interview with a candidate patient. Patients must meet ALL general inclusion criteria to participate in the Registry. If ANY general exclusion criteria are met, the patient is excluded from the Registry and cannot be enrolled (recruitment failure).

### **5.3.2 Inclusion Criteria**

#### **5.3.2.1 General Inclusion Criteria**

1. Subject was treated or is expected to be treated for acute/subacute thrombosis, as determined by the investigator, in the peripheral vasculature with the JETi Hydrodynamic Thrombectomy System.
2. Subject or legally authorized representative must provide written informed consent.
3. Subject must be  $\geq 18$  years of age.

### **5.3.3 Exclusion Criteria**

#### **5.3.3.1 General Exclusion Criteria**

1. Subject has previously been registered in the JETi Registry in the last 12 months unless treated in the contralateral limb/different anatomy; patients treated in the contralateral limb/different anatomy within the last 12 months may re-enroll in the study.
2. Subject is currently participating in another drug or device clinical investigation.
3. Subject has active symptoms and/or a positive test result of COVID-19 or other rapidly spreading novel infectious agent within the past 20 days.

## **5.4 Subject Enrollment**

A patient is considered enrolled in the Registry from the moment the patient provides written informed consent.

All patients treated with the JETi System and for which study consent is obtained, will be consecutively enrolled in the study.

## 5.5 Subject Registration

An enrolled subject is considered registered in the Registry only after a JETi Catheter is introduced into the intended vasculature of the subject during the procedure (Day 0). Patients may be consented up to 5 days post-JETi procedure. A subject who is enrolled but not registered in this study will be considered a screen failure. The sample size of the Registry is based on the number of registered subjects.

## 5.6 Subject Withdrawal and Discontinuation

Each registered subject shall remain in the Registry until completion of the required follow-up period; however, a subject's participation in any registry is voluntary and the subject has the right to withdraw at any time without penalty or loss of benefit. Conceivable reasons for discontinuation may include, but not be limited to, the following:

- Subject death
- Subject voluntary withdrawal
- Subject lost-to follow-up as described below
- Subject's follow-up is terminated according to **Section 3.3**.

Sites must notify the Sponsor of the reason(s) for subject discontinuation. Investigators must also report this to their respective IRB/EC as defined by their institution's procedure(s).

No additional follow-up is required, or data recorded from subjects once withdrawn from the Registry, except for the status (deceased/alive).

However, if a subject withdraws from the Registry due to problems related to the safety or performance of the JETi System, the investigator shall ask for the subject's permission to follow his/her status/condition outside of the Registry.

In case of subject withdrawal of consent, the site should make attempts to schedule the subject for a final Registry visit. At this final follow-up visit, the subject will undergo clinical assessment.

### Lost-to-Follow-up

If the subject misses both scheduled follow-up time points and the attempts at contacting the subject detailed below are unsuccessful, then the subject is considered lost-to-follow-up. Site personnel shall make all reasonable efforts to locate and communicate with the subject (and document these efforts in the source documents), including the following, at each contact time point:

- A minimum of two telephone calls on different days over the specified follow-up windows to contact the subject should be recorded in the source documentation, including date, time and initials of site personnel trying to make contact.
- If these attempts are unsuccessful, the site should send a letter (certified if applicable) to the subject.
- If a subject misses one follow-up contact time points, it will be considered a missed visit. The subject may then return for subsequent visits. If the subject misses two consecutive time points

and the above-mentioned attempts at communicating with the subject are unsuccessful, the subject will be considered lost-to-follow-up.

**Note:** Telephone contact with General Practitioner, non-Registry cardiologist or relative without the presence of the subject or indirect documentation obtained via discharge letters will be considered as subject contact for the purpose of collecting vital status information. The center shall retain records of the contact.

## 5.7 Number of Subjects

The Registry will register approximately 280 subjects.

## 5.8 Total Expected Duration of the Clinical Investigation

The expected duration of each subject's participation is approximately 12 months, including the scheduled visits and data collection for this registry that will occur at 30 days, and 12 months. Subjects will exit the registry at the end of their 12-Month Follow-Up visit.

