#### 3.1 **Clinical Investigation Procedures and Follow-up Schedule**

The study flowchart is shown in **Figure 1**, and the follow-up requirements are described in this Section. After meeting all eligibility criteria, a subject is considered enrolled in the registry from the moment the subject provides written informed consent. The point of registration in the registry is when a JETi Catheter is introduced into the intended vasculature of an enrolled subject during the procedure (Day 0). A subject who is enrolled but not registered in this study will be considered a screen failure. Consenting up to 5 days after the JETi procedure is acceptable. In these cases, the point of registration will be the same and any procedural information will be entered post-consent, and adverse events (AEs) will be collected retrospectively from the point of registration (Day 0). Any assessments performed prior to consent will be conducted per standard of care and data collection will occur after consent is obtained. Any assessment performed after consent will be conducted per the protocol's requirements. Registered subjects' data will be collected at baseline, procedure, and discharge, as well as at 30 days (-20 days/+30 days), and 12 months (-5 months/+1 month) after the JETi procedure.

For all follow-up visits, if all attempts to have the patient return to the office for an in-office visit are unsuccessful, a phone call or virtual follow-up will be allowed to collect available data. Protocol deviations must be reported for data that could not be collected via phone.

Refer to the detailed follow-up schedules in **Section 6.1.6** and **6.2.6**.

Figure 1: Study Flowchart

\*Consenting up to 5 days after the JETi procedure is acceptable.

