### 4.2.2 Arterial Subjects

- Clot removal grade for each JETi-treated target vessel from pre-JETi angiogram to final angiogram (post-JETi thrombectomy and after any/all adjunctive therapies and prior to removal of the vascular sheath) per the grades in **Table 1**.
- Components of the MAE including device-related death, major amputation of treated limb (arterial subjects only), and major bleeding up to 30 days post-JETi as adjudicated by a CEC.
- Ankle Brachial Index\* (ABI) of treated limb(s) at baseline and 30 days.
- Rutherford\* classification at baseline and 30 days.  
*\* only applicable to subjects with lower limb arterial thrombus*
- Rate of re-thrombosis of JETi-treated vessel at 30 days, and 12 months, as assessed by investigator/physician reported.

- Patency as determined by duplex ultrasound at baseline 30-day, and 12-month follow-up. Note that this endpoint will only apply to subjects treated for arteriovenous thrombus.
- Vessel patency: assessed by the independent imaging core laboratory using the Modified Thrombolysis in Myocardial Infarction (TIMI) classification called TIPI (Thrombo-aspiration in Peripheral Ischemia) (Table 3) for each JETi-treated vessel, assessed using angiogram
  - At post-JETi timepoint (post-JETi thrombectomy and prior to any adjunctive therapies to treat underlying culprit lesions)
  - At final timepoint (post-JETi thrombectomy and after any/all adjunctive therapies and prior to removal of the vascular sheath)

If no adjunctive therapies or devices are used after JETi, post-JETi TIPI score is also final TIPI score.

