### 6.1.4 Follow-up

A window of 10 days to 60 days post JETi procedure is allowed for the 30-day follow-up visit (30 days - 20 days/+30 days), and a window of 5 months to 13 months is allowed for the 12-month (12 months -5 months/+ 1 month) follow-up visit.

- An in-office visit is required for 30-day follow-up visit. If all attempts to have the patient return to the office for an in-office 30-day follow-up visit are unsuccessful, a phone call follow-up will be allowed to collect SF-12 and adverse event data. Protocol deviations will need to be reported for data that could not be collected via phone.
- While an in-person visit is strongly recommended, the follow-up assessments at 12 months may be collected by phone call or virtual visit. Protocol deviations will need to be reported for data that is not collected via phone.

The following data will be collected at the follow-up visit:

- Adverse events
- Medications: Anticoagulant and antiplatelet medications
- ABI\* (30-day visit only)
- Rutherford classification\* (30-day visit only)

\* Note: ABI and Rutherford assessment can be obtained via a non-study physician, including a referring physician; this will not be considered a protocol deviation. ABI and Rutherford are only applicable to lower limb arterial thrombosis.

- QoL questionnaire (SF-12)

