### 6.2.4 Follow-up (Office Visit)

A window of 10 days to 60 days post JETi procedure is allowed for the 30-day follow-up visit (30 days - 20 days/+30 days), and a window of 7 months to 13 months is allowed for the 12-month (12 months -5 months/+1 month) follow-up visit.

- An in-office visit is required for 30-day and 12-month follow-up visit. If all attempts to have the patient return to the office for an in-office visit are unsuccessful, a phone call follow-up will be allowed to collect applicable data. Protocol deviations will need to be reported for data that could not be collected via phone.

The following data will be collected at the follow-up visit:

- Adverse events
- Medications: Anticoagulant and antiplatelet medications
- Leg pain assessment by 7-point Likert Scale
- DUS \*
- Villalta PTS assessment \*
- QoL questionnaire: SF-12 \*

*\* can be obtained via a non-study physician, including a referring physician. This will not be considered a protocol deviation*

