## 7.3 Adverse Event and Device Deficiency/Device Malfunction Reporting

### 7.3.1 Adverse Event Reporting

Safety surveillance and reporting starts as soon as the JETi catheter is introduced into the intended vasculature during the procedure. AEs will not be collected for screen failure subjects. Safety surveillance and reporting will continue until sites perform the last follow-up visit, the subject is deceased, the subject concludes participation in the registry, or the subject withdraws from the registry. Sites will collect all serious adverse events, all JETi device related adverse events, including deaths and device deficiency data throughout the period defined above and will report these events to the Sponsor on a CRF. Sites should update additional information regarding an adverse event on the appropriate CRF.

[figure not shown]
Unchanged, chronic, non-worsening or pre-existing conditions are not AEs and should not be reported.

[figure not shown]
The Sponsor will provide an offline form to allow the investigator to report SAEs in the event the entry cannot be made in the electronic data capture (EDC). This does not replace the EDC reporting system. Sites must still enter all information in the EDC system as soon as feasible.

For the purposes of this Registry, the following adverse events will be reported for each subject through the 12-month follow-up visit.

- All device- and procedure-related AEs
- All SAEs

In addition, the following adverse events regardless of seriousness or relatedness will be collected:

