1.4.2.3 Venous Subjects

- Percent of treated vessels with ≥75% clot reduction from pre-JETi venogram to post-JETi venogram (post-JETi thrombectomy and before any adjunctive therapies to treat underlying culprit lesions) via modified Marder score. The independent imaging core laboratory will be responsible for assessing this endpoint.
- For subjects not treated for lower extremity DVT (i,e. upper extremity DVT (UE DVT)), Clot removal grade for each JETi-treated target vessel from pre-JETi venogram to final venogram (post-JETi thrombectomy and after any/all adjunctive therapies and prior to removal of the vascular sheath) per the grades in **Table 1**.
- Components of the JETi-related MAE including up to 30 days post-JETi adjudicated by a CEC death, symptomatic pulmonary embolism (PE), major bleeding and rethrombosis of target vessel(s).
- Re-thrombosis in the JETi-treated vessel(s) at 30-day and 12-month follow up, as assessed by investigator/physician reported, and as adjudicated by CEC.
- The Villalta Post Thrombotic Syndrome (PTS) severity scale at baseline, 30-day, and 12-month follow-up. Note that this assessment will apply only to subjects with lower extremity DVT.

Statistical Analysis Plan

- Edema component score from the Villalta Post Thrombotic Syndrome (PTS) severity scale at baseline, 30-day, and 12-month follow-up.
- A 7-point Likert Scale for leg pain at baseline, discharge, 30-day, and 12-month follow-up.
- Venous patency and compressibility as determined by duplex ultrasound at baseline, 30-day, and 12-month follow-up.
- Acute success,
 assessed by core laboratory:
 - Device success: Post-JETi thrombus removal grade II-III
 - occurs after JETi system and any other adjunctive device or procedures.
 - Procedural success: Technical success with no JETi-related MAEs within 5 days of registration or by discharge, whichever occurs first.

If no adjunctive therapies or devices are used after JETi, post-JETi is also final score

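### The 12-month visit may be held from month 7 and follow-up ends at that visit, so the descriptive 12-month event percentages mix about 7 to 13 months of observation and are expected to run low to the extent visits are early

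*Protocol*

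**What the plan says.** **Visit window.** Protocol 3.1 sets the last visit at "12 months (-5 months/+1 month) after the JETi procedure", and the schedules in Tables 5 and 6 repeat this. Protocol 6.2.4 spells it out for venous subjects: "a window of 7 months to 13 months is allowed for the 12-month" visit. Protocol 6.1.4, for arterial subjects, says "a window of 5 months to 13 months is allowed for the 12-month" visit, next to the same -5/+1 figures.

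**End of follow-up.** Protocol 5.8: "Subjects will exit the registry at the end of their 12-Month Follow-Up visit". Protocol 7.3.1: "Safety surveillance and reporting will continue until sites perform the last follow-up visit" (or until death, withdrawal or the end of participation). The same section says that "the following adverse events will be reported for each subject through the 12-month follow-up visit". All of these stop at a visit, not at a fixed day, and no later contact is described.

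**What is reported.** For arterial subjects, Protocol 4.2.2 lists "Rate of re-thrombosis of JETi-treated vessel at 30 days, and 12 months". For venous subjects, SAP 1.4.2.3 lists "Re-thrombosis in the JETi-treated vessel(s) at 30-day and 12-month follow up". For all subjects, Protocol 4.2.1 lists JETi-related AEs at discharge, 30 days and 12 months. All are descriptive endpoints.

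**How it is summarised.** SAP 3.2 gives device- and procedure-related AEs and all SAEs as numbers of events and percentages of subjects. SAP 2.3.2 says only that descriptive endpoints are summarised descriptively, and SAP 2.9 uses available data. The visible SAP shows no time-to-event method, follow-up-time denominator or analysis window.

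**The concern.** A month-7 visit complies with the protocol. It is not a deviation, it leaves no data field missing, and it satisfies the trigger for the final analysis (Protocol 8.4, SAP 2.6). But it closes the subject's record up to five months short of the stated horizon. If that subject stays in the denominator of a crude percentage, any event after the visit is in effect counted as no event.

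The window is lopsided, with five months early against one month late, so if visits spread across it the expected net effect is under-counting.

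At stake are the registry's event-based late outcomes: 12-month re-thrombosis, JETi-related AEs and SAEs. After the 30-day visit there is only one more scheduled contact, so nothing later can pick up what was missed. The 30-day outcomes do not share the problem, because surveillance continues past an early 30-day visit.

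**Working it through.** **Window.** 12 - 5 = 7 and 12 + 1 = 13. This reproduces the 7-to-13-month range in Protocol 6.2.4. It does not reproduce the 5-to-13-month range in Protocol 6.1.4.

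**Inputs.** The visit window, exit rule and surveillance rule come from the documents. The true 12-month risk R and the timing of events do not. The documents give no 12-month event rate and no visit-timing data, so both are assumptions here.

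**Formulas.** A crude percentage over subjects who exit at their visit is the average of F(t) over visit times t, where F(t) is the cumulative risk by month t.

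- Constant hazard: F(t) = 1 - (1 - R)^(t/12).
- Front-loaded: a share s of the 12-month events falls by month 1, then the hazard is constant. F(t) = 1 - (1 - sR) exp(-h(t - 1)), with h = -ln[(1 - R)/(1 - sR)]/11.

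**Worked case, R = 20%, constant hazard.**

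- All seen at month 7: 1 - 0.8^(7/12) = 1 - 0.878 = 12.2%.
- Visits uniform over months 7 to 13: with h = -ln(0.8)/12 = 0.0186, the average is 1 - [0.8^(7/12) - 0.8^(13/12)]/(6h) = 1 - (0.8779 - 0.7853)/0.1116, which gives 16.9%.

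**By event pattern, R = 20%.**

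| Event pattern | All at month 7 | Uniform 7-13 | Uniform 12-13 |
|---|---|---|---|
| Constant hazard | 12.2% | 16.9% | 20.7% |
| Half of events by month 1 | 15.6% | 18.3% | 20.4% |
| 80% of events by month 1 | 18.2% | 19.3% | 20.2% |

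**By share seen early** (constant hazard, share p at month 7, the rest at month 12): the reading is p × 12.2% + (1 - p) × 20%.

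- p = 10%: 19.2%
- p = 25%: 18.1%
- p = 50%: 16.1%

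**Other true risks**, all seen at month 7, constant hazard: 5% reads 2.9%, 10% reads 6.0% and 30% reads 18.8%. The relative loss is about 37% to 41%.

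**Arterial wording.** If the month-5 limit in Protocol 6.1.4 applied and all were seen then: 1 - 0.8^(5/12) = 8.9% against a true 20%.

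**Would Kaplan-Meier alone repair it?** Take R = 20%, constant hazard, visits uniform over 7 to 13, and censoring at the visit. If every event carries its true onset date, the month-12 estimate is 20%. Venous re-thrombosis may, however, first be found on the duplex scan scheduled at that same visit. If such events are dated at the visit, and none was detected earlier at the 30-day scan, a simulation gives about 22% with a quarter of events so dated, 24% with half and 27% with all. The estimate then errs upward, and with half or more of events so dated the error exceeds the 3-point shortfall of the crude figure.

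**The case against.** The case for leaving the plan alone has real substance.

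- **A wide window is a reasonable choice** for a post-market, real-world registry. The affected outcomes are all descriptive, and the primary endpoints are procedural or end at 30 days. This stands, and it limits the weight of the point.
- **A reader might infer that events between months 7 and 12 are never collected.** The documents do not support that. The loss applies only to subjects seen early, and only from their own visit to month 12. Someone seen at month 12 or 13 has those months covered.
- **A reader might infer that the error always favours the device.** It need not. Visits after month 12 add follow-up and push the percentage slightly up (20.2% to 20.7% in the table). The net direction depends on visit timing, which is unknown.
- **These are not the only 12-month durability data.** Duplex patency, Villalta, leg pain and SF-12 are also collected. They measure status at the visit, so the gap after the visit does not touch them, though they too are taken at varying times.
- **The analysis rule may exist out of sight.** SAP 2.2.2 is blank in the public copy and section numbers are skipped, so a denominator or time-to-event rule could be there. Several endpoints are also labelled by visit rather than by calendar month. This is a fair limit on any claim about the analysis. It does not answer the collection gap, which lies in unredacted protocol text: no analysis rule recovers events that were never recorded.

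**Conclusion.** The point holds in a limited form. For subjects seen early within the permitted window, events between the visit and month 12 are not collected. The descriptive 12-month re-thrombosis, JETi-related AE and SAE percentages therefore mix about 7 to 13 months of follow-up. They are expected to be biased low to the extent that visits are early.

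The size runs from negligible to roughly 40% in relative terms. The upper end needs every subject seen at month 7 under a constant hazard. Even spreading of visits takes an assumed 20% to about 17%, or to about 18% with half of events in the first month. These figures rest on assumed risks, event timing and visit timing.

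The 5-month and 7-month lower limits contradict each other and must be reconciled. The point stands under either.

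**What to change.** **Protocol 5.8 and 7.3.1.** Keep the visit window for duplex, Villalta and SF-12, but separate it from exit. A subject whose 12-month visit falls before day 365 would exit only after a phone or record contact on or after day 365, covering AEs, symptomatic re-thrombosis and vital status. The protocol already accepts phone follow-up.

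**Protocol 3.1, 6.1.4, 6.2.4 and Tables 5 and 6.** Reconcile the stated windows.

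**SAP.**
- Report the distribution of visit timing and the number followed to day 365.
- Estimate event rates at day 365 by a time-to-event method censored at last contact, using onset dates for clinically dated events.
- Treat re-thrombosis first found on the visit scan separately, as status at the visit or as interval-censored.
- Handle death as a competing event.
- If a rule of this kind already sits in the redacted text, confirm it.

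**If no amendment is wanted.** Label the rates by actual follow-up, for example as events through the 12-month visit at months 7 to 13, and show the follow-up distribution. This discloses the gap but does not close it.

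**Cost.** One short contact for each early-visit subject, some added SAP text and tables, and probably slightly less favourable reported rates.
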